### 9.2. Study Intervention Packaging and Labeling

The label will have the following language:

- Sponsor name and that it is for investigational use only for this study.
- The software will have its own unique identifier and a kit Number will be on the device box.
- Instructions will be included in the kit and a video for onboarding.

### 9.3. Dispensing Investigational Intervention

An Interactive Web Response System (IWRS) will be used to manage subject screening and randomization.

BVR-100 and BES-100 VR device kit Numbers will be assigned by the IWRS based on the treatment schedule.

The assigned study device will be shipped directly from the depot to the subject, and the delivery/receipt will be confirmed by the unblinded site support team during the introductory call. The VR intervention subject onboarding will be completed independently by the subject during the second part of the Baseline visit via an onboarding video and ongoing technical support provided by unblinded site support team external to the site.

Subjects will engage with the VR intervention for at least 3 VR sessions per week, for a period of 8 weeks.

#### **9.4. Study Intervention Accountability**

The unblinded site support team external to the investigator site is responsible for maintaining adequate and up to date records of VR device accountability documentation that includes the date of shipment out of the depot, delivery/receipt by subject, and shipment back to depot/receipt at depot in the study records for each subject. The contract research organization (CRO) will maintain a master accountability log.

## 10. TREATMENT OF SUBJECTS

### 10.1. Investigational Intervention

BVR-100 or BES-100 will be shipped directly to the address of eligible subjects. Onboarding and training videos will be provided electronically.

### 10.2. Compliance with the Investigational Intervention

Use of BVR-100 or BES-100 will be recorded electronically and closely monitored by the unblinded site support team for protocol compliance. Weekly reminders will be sent out to study subjects, and they will be followed up with as necessary.

### 10.3. Concomitant Medications and Therapies

Prior medications, including the use of psychotropic medication taken during the previous 12 months, and any other medication taken during the previous 3 months will be recorded at Screening. Details on all medications taken prior to Screening (including dosing changes) will be recorded based on subject report.

Thereafter, any changes in concomitant medications or new medications added until the end of study will be recorded. At a minimum, the following information on prior and concomitant medications will be recorded on the case report form (CRF): medication name, dose, frequency, route, start date and time, stop date and time, and indication.

#### Prohibited Medications

Psychotropic medications and medications with a propensity for psychotropic effects are not permitted during the study participation, except as discussed below (see Allowed Concomitant Psychotropic Medication). Subjects will be requested to refrain from using benzodiazepines (eg, clonazepam and bromazepam) for the duration of their participation in the study. The use of herbal supplements, dietary supplements or other complementary or alternative medications for treating psychiatric indications, as well as nutritional supplements and nonprescription herbal preparations with CNS effects (eg, St. John's Wort, omega-3 fatty acids, kava extracts, gamma-aminobutyric acid supplements, cannabidiol, etc) are not permitted during the study participation. Disallowed psychotropic medications must be washed out during the screening/washout period and fully discontinued a minimum of 3 days or 5 half-lives (whichever is longer) prior to randomization. Disallowed herbal supplements with CNS-related indications must be fully discontinued a minimum of 3 days prior to randomization.

#### Allowed Concomitant Psychotropic Medications

The use of concomitant psychotropic medications at a stable dose for at least 3 months prior to Screening will be permitted provided they are prescribed for non-exclusionary indications. Pharmacological treatment and dose should not change during trial unless required by physician to adequately treat the subject.

#### Treatment of Insomnia

Concomitant use of eszopiclone, zaleplon, zolpidem and zolpidem CR is permitted at the discretion of the Investigator with the following restrictions:

- eszopiclone ( $\leq 3$  mg/day), zopiclone ( $\leq 7.5$  mg/day), zaleplon ( $\leq 20$  mg/day), zolpidem ( $\leq 10$  mg/day), and zolpidem CR ( $\leq 12.5$  mg/day) may be administered at bedtime for insomnia, not exceeding 3 instances per week.

Diphenhydramine  $\leq 100$  mg/day and melatonin  $\leq 10$  mg/day may be administered at bedtime for insomnia, as needed. Over-the-counter melatonin may be used. Combination melatonin products are not allowed.

Medications that are used for insomnia should be administered no more than once nightly and should not be used in combination.

The date and time of the last dose of any concomitant psychotropic medication(s) taken prior to scheduled effectiveness assessments must be recorded at each visit. Subjects should be encouraged to avoid taking any psychotropic medication (or any agents that may cause sedation) within 12 hours of effectiveness assessments.

#### Allowed Concomitant Non-Psychotropic Medications

Non-psychotropic medications used to treat stable, chronic medical conditions or for short-term treatment of an acute medical condition may be used during screening and throughout participation. Use of non-prescription pain medications (eg, aspirin, acetaminophen/paracetamol) are allowed during all phases of the study.

Subjects will be requested to refrain from using benzodiazepines (eg, clonazepam and bromazepam) and acute use of beta-blockers (eg, atenolol and propranolol) for the duration of their participation in the study. Individuals with a stable history of beta-blockers for cardiac indications are permissible for this study.

Subjects will be requested to refrain from use of alcohol, tetrahydrocannabinol (THC) for any purpose while taking part in the study.

The use of any concomitant medication or other psychotropic drug use will be assessed and registered during all scheduled telephone visits.

Information on the format and version of the coding dictionary is provided in the Data Management Plan (DMP). All medications will be coded using World Health Organization Drug Dictionary (WHO-DD).

## 11. STUDY ASSESSMENTS

All study assessments will be conducted/Performed remotely. A study schematic is presented in [Table 5](#). A Schedule of Assessments to be performed each week is presented in [Table 2](#).

### 11.1. Demographics and Baseline Characteristics

Demographics will be recorded, including: year of birth and age, sex assigned at birth, ethnic identity, and racial identity.

### 11.2. Medical and Psychiatric History

Medical and psychiatric history will also be recorded. Psychiatric history will be reviewed, and diagnoses will be confirmed by PI using the MINI. Prior experience with CBT (ie, including questions about experiences with in-*imagination* or in-*vivo* exposure to fearful situations) and use of concomitant medications and substance use will be reviewed. Only relevant/significant medical history and recurrence of any condition will be collected.

The MINI ([Sheehan-1998](#)) is a short diagnostic structured interview to explore 17 disorders based on DSM-V criteria. There are one or two questions for each disorder, which can be ruled out as diagnoses based on negative responses. All eligible Subjects must meet the MINI criteria for Social Anxiety Disorder for study inclusion.

### 11.3. Effectiveness Assessments

All assessments will be administered as outlined in Table 2, Schedule of Assessments. Descriptions of each assessment are outlined below.

#### 11.3.1. Credibility/Expectation Questionnaire

The Credibility/Expectation Questionnaire (CEQ), ([Devilly-2000](#)) asks about the improvements that subjects believe will be achieved as a result of treatment, and how believable, convincing, and logical the treatment seems. It contains six items rated on a 1–9 or a 0%–100% scale. The first three items of the scale load onto the credibility factor and the final three items load onto the expectancy factor.

#### 11.3.2. Liebowitz Social Anxiety Scale

The LSAS (Liebowitz-1987) is a clinician administered instrument that assesses both fear and avoidance across a number of social situations. This measure has been frequently used in pharmacological studies of social phobia and in cognitive behavioral studies.

The scale consists of 24 items each depicting different social situations. The fear scale ratings range from 0 (no fear) to 3 (severe fear). The avoidance ratings also range from 0 to 3 and are based on the percent of time avoiding the particular situation [0 = never; 1 = occasionally (10%); 2 = often (33–67%); and 3 = usually (67–100%)]. The clinician has the flexibility to ask additional questions beyond these ratings and may adjust the ratings accordingly. In addition to the fear and avoidance subscales, the LSAS is further divided into two subscales for scoring, including social interaction (11 items) and performance situations (13 items). Thus, an overall score is derived along with six additional scores based on fear and avoidance: total fear, fear of

social interaction, fear of performance situations, total avoidance, avoidance of social interaction, and avoidance of performance situations.

#### **11.3.3. Clinical Global Impression - Severity**

The severity of illness for each subject will be rated using the CGI-S ([Guy-1976](#)). The CGI-S is a standardized, clinician-administered global rating scale that measures disease severity on a 7-point Likert scale. A higher score on the CGI-S represents a higher severity of disease. To perform this assessment, the rater or investigator will answer the following question: "Considering your total clinical experience with this particular population, how mentally ill is the patient at this time?" Response choices include: 1 = normal, not at all ill; 2 = borderline mentally ill; 3 = mildly ill; 4 = moderately ill; 5 = markedly ill; 6 = severely ill; and 7 = among the most extremely ill patients.

#### **11.3.4. Clinical Global Impression - Improvement**

The efficacy of trial treatment will be rated for each subject using the CGI-I ([Guy-1976](#)). The rater or investigator will rate the subject's total change compared to the subject's condition at baseline, whether or not it is due entirely to study treatment. Response choices include: 1 = very much improved, 2 = much improved, 3 = minimally improved, 4 = no change, 5 = minimally worse, 6 = much worse, and 7 = very much worse.

#### **11.3.5. Patient Health Questionnaire**

The PHQ ([Spitzer-1999](#)) is a self-administered version of the PRIME-MD diagnostic instrument for common mental disorders. The PHQ-9 is the depression module, which scores each of the 9 DSM criteria as "0" (not at all) to "3" (nearly every day).

#### **11.3.6. Patient Global Impression Improvement**

The PGI-I ([Guy-1976](#)) will ask subjects to rate their perceived improvement of their condition from treatment initiation to present, based on the following seven-point scale: 1=very much improved since the initiation of treatment; 2=much improved; 3=minimally improved; 4=no change from baseline (the initiation of treatment); 5=minimally worse; 6= much worse; 7=very much worse since the initiation of treatment.

#### **11.3.7. Qualitative Interview**

At the conclusion of the study (EOS) or early termination (ET), a member of the unblinded site support team will complete a qualitative interview within 48 hours of the final clinical assessments outlined above. This interview will explore subjects' experiences, perceptions, and acceptability of BVR-100 and BES-100. This interview will last for approximately 45 minutes.

### **11.4. Safety Assessments**

The Investigator or appropriate designee will review results of safety assessments on a regular basis and the Sponsor must be kept fully informed of any clinically significant findings either at Screening or subsequently during study conduct. Subjects will be provided a contact telephone number to report safety concerns (eg, AEs). This telephone number will be the study site's phone number and also documented on the informed consent form (ICF).

Safety assessments will be administered according to the Schedule of Assessments in [Table 2](#).

### **11.4.1. Adverse Events**

Adverse events will be collected for each subject. Subjects should be queried in a non-leading manner, without specific prompting (eg, “Has there been any change in your health status since your last visit?”). See [Section 12](#), Safety Reporting.

All AEs will be monitored throughout the study by spontaneous subject reports and by the investigator site staff soliciting AEs at each scheduled telephone contact.

### **11.4.2. Columbia Suicide Severity Rating Scale**

The Columbia Suicide Severity Rating Scale (C-SSRS) will be administered by investigator site staff.

The C-SSRS is a tool designed to systematically assess and track suicidal adverse events (suicidal behavior and suicidal ideation) throughout the trial. The strength of this suicide classification system is in its ability to comprehensively identify suicidal events while limiting the over-identification of suicidal behavior. The scale takes approximately 5 minutes to administer ([Posner-2011](#)). The C-SSRS will be administered by a trained rater at the site. Subjects with Type 4 or Type 5 suicidal ideation at the Screening or Baseline visit will be excluded from entry into the study. Subjects with Type 4 or Type 5 suicidal ideation during the study will be discontinued from the study and referred to a mental health professional. At the Screening visit/Visit 1, the “Baseline/Screening” version of C-SSRS will be used. For all applicable visits onward, the “Since Last Visit” version of the C-SSRS will be used.

If a subject answers “yes” to “Suicidal Ideation” Item 4 (active suicidal ideation with some intent to act, without specific plan) or Item 5 (active suicidal ideation with specific plan and intent) on any post-Baseline C-SSRS assessment, the subject must be discontinued from the study, referred to the Investigator for follow-up evaluation, and followed until the event resolves; in addition, an associated AE must be reported.

## **11.5. Study Visits and Assessments**

This study is a decentralized trial, and thus all ‘visits’ will occur via telehealth. All assessments will be completed in accordance with the schedule outlined in Table 2.

### **11.5.1. Visit 1 - Screening: (Up to 14 Days)**

Subjects will be evaluated at Screening (up to 14 days prior to Randomization) to determine their eligibility to randomize in the study.

The following study-related procedures will be performed by investigator site staff in order of the site’s clinical preference:

- Obtain informed consent. (**MUST occur first**)
- Review inclusion and exclusion criteria.
- Record demographics and baseline characteristics.
- Record medical/psychiatric history.

- Administer the MINI.
- Clinician administers the LSAS.
- Clinician administers the C-SSRS.
- Subject completes the PHQ-9.
- Review prior/concomitant medications.
- Review pretreatment adverse event monitoring.

For subjects that wish to participate in the study and are currently taking disallowed psychotropic medications or herbal supplements, subjects will be asked to wash-out from these medicaments during the Screening period.

#### **11.5.2. Visit 2 - Randomization (up to 7 days)**

After Screening, subjects deemed eligible by the Investigator will be contacted by investigator site staff to be informed they are qualified to participate in the study. Visit 2 will occur up to 7 days prior to Baseline, including the following study-related procedures to be performed by investigator site staff:

- Review Inclusion and Exclusion criteria.
- Confirm continued Subject interest in study participation.
- Review prior/concomitant medications.
- Pretreatment adverse event monitoring
- Randomization via an interactive web responses system (IWRS) in a 1:1 ratio to either treatment (BVR-100) or control (BES-100) intervention
- Schedule Baseline visit within 5-7 days of the Randomization visit.

Remind the subject that neither the investigator site staff nor the subject will know which treatment group they have been assigned to throughout the duration of their participation, and that they must not discuss anything regarding the intervention with the investigator site staff.

Remind the subject that they will be contacted by a designated member of the unblinded site support team to provide guidance shortly after device delivery.

After randomization to either treatment group, the VR headset—pre-loaded with BVR-100 or BES-100 will be shipped out to the subject's address from the depot.

Subjects will be blinded to their intervention assignment, and they will be instructed on an ongoing basis to refrain from sharing any details about their intervention with anyone beyond the unblinded site support team assigned to the study.

#### **11.5.3. Visit 3 - Baseline: (Week 1)**

The Baseline visit will be scheduled to occur within 5-7 days of the randomization visit, to allow adequate time for VR device delivery/receipt. However, if the device is received earlier and the Baseline visit occurs earlier, this will be acceptable. If, due to delays with device

delivery/receipt, an extension beyond the 7 days is necessary, approval by the Medical Monitor is required.

Upon confirmation of device delivery, a member of the unblinded site support team will contact the subject to confirm receipt of the device, to establish a relationship, and again remind the subject that they would be the only contact for any device related issues throughout the duration of their participation in the study. After this is confirmed, the Baseline visit with the investigator site staff could take place.

The Baseline visit is the first day of Week 1, and it will be split into two separate parts, expected to occur on the same day. During the first part of the Baseline visit, a telehealth call will be performed with the investigator site staff who will administer Baseline visit (Day 1) assessments including the following procedures:

***PART 1 (investigator site staff during telehealth Visit 3):***

- Clinician administers C-SSRS.
- Clinician administers LSAS.
- Clinician administers CGI-S.
- Collect any AEs.
- Review concomitant medication changes.
- Subject completes PHQ-9.
- Prior to ending the telehealth visit, remind the subject regarding Part 2 of the visit, which is completed independently at home by the subject, where they will be responsible for three activities:
  - Viewing the video for VR onboarding, a link for which will be sent immediately following the conclusion of Baseline, Part 1;
  - Completing the first VR session; and
  - Completing (electronically) the CEQ.

Remind the subject that throughout the duration of their study participation, they must not discuss anything regarding the intervention with the investigator site staff and that they could reach out to the designated unblinded site support team at any time.

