After the VR sessions have been completed, subjects are requested to complete the PROs (PHQ-9, PGI-I, and CEQ) as applicable to each particular week, electronically as specified in the Schedule of Assessments. The scales should be reviewed on a bi-weekly basis, to ensure completeness, for any potential AEs that may be reported, and retraining provided to subjects as necessary. During the last 3 days of Weeks 2, 4, 6, and 8 (EOS/ET), investigator site staff will conduct telehealth study visits to collect clinician-administered outcome measures (C-SSRS, LSAS, CGI-S, CGI-I), AEs and concomitant medication changes. For the Week 8 (EOS/ET) visit, an additional qualitative interview with a member of the unblinded site support team will occur to explore each subjects' experience with their respective interventions (BVR-100 or BES-100). All attempts will be made to ensure that each subject is assessed by the same investigator site staff to minimize confounding bias related to changing assessor. In the event that subjects require technical support or further program instructions, support will be provided by the unblinded site support team not involved in data collection.

All AE data will be collected by investigator site staff during the check-ins and recorded in the electronic data capture (EDC). Subjects will be provided with contact information in the informed consent form to facilitate ready access to the site/Investigator in order to help address potential safety issues that may arise and to facilitate AE reporting.

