### **7.2.2. Blinding**

Subjects, Investigators, investigator site staff, persons performing the assessments, clinical operations personnel, data analysts, will remain blinded to the identity of the VR intervention from the time of randomization until database lock and unblinding, using the following methods:

- Randomization data are kept strictly confidential until the time of unblinding in the IWRS, and will not be accessible by anyone else involved in the study with the

following exceptions: Unblinded site support team to support the subjects with any technical VR device issues and performing qualitative interview, pharmacovigilance department for evaluation and reporting of UADEs, SAEs, and any other AEs of clinical interest.

- The identity of the interventions will be concealed by the use of VR headsets that are all identical in packaging, labeling, schedule of administration and appearance.

In order to secure subject blinding, subjects will have no prior experience with CBT. Subjects will be instructed and reminded on an ongoing basis not to share descriptions of the intervention they are receiving in any capacity with investigator site staff (with the exception of the unblinded site support team) during visits or at any point during study participation and discouraged from discussing details of the therapy outside the study.

Investigator site staff will not be provided the details of the study intervention and various components/experiences within the program beyond the broad overview that is presented in this protocol to minimize any chance of unblinding. The VR device allocated to each subject upon randomization will be shipped directly to the subject's address from the depot and any activities, including subject training/tech support related to the VR intervention will be managed by the unblinded site support team external to the site, removing the investigator site staff from the entire process to minimize any chance of unblinding.

Actual subject identity revealing actual study treatment will not be disclosed before database lock and study unblinding unless an emergency unblinding becomes necessary.

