#### **11.5.5. Intervention Period (Weeks 3, 5, and 7)**

Independently at home by subject:

- Minimum of 3 required VR sessions.
- Subjects are encouraged to engage with optional content and to review content completed at any time.
- In the event that subjects require technical support or further VR program instructions, support will be provided by a designated unblinded site support team (ie, personnel external to the site and not involved in data collection).

There are no telehealth visits scheduled during these weeks; however, unscheduled telehealth visits to complete/perform additional safety assessments, may be conducted as deemed necessary by the investigator site staff/subject.

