## 12. SAFETY REPORTING

### 12.1. Definitions

#### 12.1.1. Adverse Events

An adverse event (AE) is any untoward medical occurrence associated with the use of an investigational intervention in humans, whether or not considered related to the intervention.

Untoward medical occurrences that occur after the time of signing the Informed Consent Form (ICF) and prior to the first VR session are a subset of AEs referred to in analysis as pre-treatment events. Those that occur after first VR session are considered AEs. Importantly, all AEs, including pre-treatment events, are collected via the same form by investigator site staff, who will complete the AE form in the EDC, which will then immediately notify both the CRO and Sponsor.

An AE can, therefore, be any unfavorable and unintended sign (including an abnormal laboratory finding), symptom, or disease occurring after the administration of an investigational intervention, whether or not considered related to the investigational intervention. AEs may include the onset of new illness and the exacerbation of pre-existing conditions. AEs will be collected from after first use of the investigational intervention to the EOS/ET.

The Investigator should attempt to establish a diagnosis of the event based on signs, symptoms, and/or other clinical information. In such cases, the diagnosis should be documented as the AE and not the individual signs/symptoms.

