## **12.2. Collection and Recording of Adverse Events**

All pre-treatment events and AEs including UADEs must be recorded in the subject's study records/source documents in accordance with the Investigator's normal clinical practice. All pre-treatment events and AEs must be recorded on the CRF.

All AEs will be followed until resolution, stabilization of the condition, the event is otherwise explained, the completion of the study, or the subject is lost to follow-up.

Each AE is to be evaluated for duration, severity, frequency, seriousness, action taken with the investigational intervention, outcome, and causal relationship to the investigational intervention. Definitions for severity, frequency, action taken with the investigational intervention, outcome, and causal relationship to the investigational intervention are presented below.

The severity of AE:

- **Mild** - Ordinarily transient symptoms that do not influence performance of subject's daily activities. Other treatment is not ordinarily indicated.
- **Moderate** - Marked symptoms sufficient to make the subject uncomfortable. Moderate influence on performance of subject's daily activities. Other treatment may be necessary.
- **Severe** - Symptoms cause considerable discomfort. Substantial influence on subject's daily activities. May be unable to continue the study, and other treatment may be necessary.

The frequency of AE:

- **Once** – an isolated episode.
- **Intermittent** – occurs on two or more separate occasions.

- **Continuous** – does not abate from date of onset to date of resolution.

The action taken with the investigational intervention:

- **None**
- **Removed temporarily**
- **Removed permanently**
- **Replaced**
- **Action taken with component(s)**
- **Unknown**

The outcome of the AE:

- **Recovered/Resolved**
- **Recovering/Resolving**
- **Not Recovered/Not Resolved**
- **Recovered/Resolved with Sequelae**
- **Fatal**
- **Unknown**

The causal relationship of the AE to the investigational intervention:

- **Not related:** - Improbable temporal relationship and is plausibly related to other drugs/products or underlying disease.
- **Related**
  - **Possible** - occurred in a reasonable time after the use of the intervention, but could be related to concurrent drugs or underlying disease.

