### **12.3.2. Unanticipated Adverse Device Effects**

The investigator or study staff must determine if an incident, experience, outcome, or adverse event that meets all the criteria for a UADE requires prompt reporting to the Sponsor and the IRB. The assessment of whether an incident, experience, outcome, or adverse event is unexpected (in terms of nature, severity, or frequency) should consider the following: the research procedures that are described in the protocol-related documents, such as the informed consent document, IRB approved research protocol, and the characteristics of the subject population being studied.

In assessing whether an incident, experience, outcome, or adverse event is related to the intervention, the investigator should consider the intervention being administered, and the underlying disorder or condition of the subject, and other circumstances unrelated to either the intervention or any underlying disorder.

UADEs and adverse events that are determined to be at least partially caused by the intervention are considered related to participation in the study, whereas adverse events determined to be solely caused by a subject's underlying disorder or other circumstances unrelated to the trial are considered unrelated to participation in the study.

The investigator is required to submit a report of a UADE to the Sponsor and the reviewing IRB as soon as possible, but in no event later than 10 working days after the investigator first learns of the event. UADEs that require remedial action to prevent an unreasonable risk of substantial harm to the public should be reported by the Investigator within 5 calendar days. The investigator is also responsible for providing progress reports on anticipated and unanticipated adverse device effects at regular intervals, but at least annually, to Sponsors, monitors, and IRBs. On the other hand, the Sponsor must immediately conduct an evaluation of a UADE and must

report the results of the evaluation to FDA (if applicable), all reviewing IRBs, and participating investigators within 10 working days after the Sponsor first receives notice of the effect. If a Sponsor determines that a UADE presents an unreasonable risk to subjects, the Sponsor must terminate all investigations within 5 days of the Sponsor making this determination.

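### The scripted reminder not to discuss the intervention with site staff has no exception for symptoms, which puts the capture and attribution of non-serious VR-related adverse events at risk

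*Protocol*

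**What the plan says.** **What subjects are told.** Protocol 11.5.2 (Randomization) and 11.5.3 (Baseline, Part 1) have site staff remind the subject that "they must not discuss anything regarding the intervention with the investigator site staff". Section 11.5.2 adds that details of the intervention may be shared only with the unblinded support team. Section 7.2.2 is narrower: subjects are told "not to share descriptions of the intervention they are receiving in any capacity with investigator site staff". Section 7.1 also limits the ban to descriptions. When the support team confirms delivery of the headset, it reminds subjects that "they would be the only contact for any device related issues throughout the duration of their participation in the study" (11.5.3).

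**Who collects and judges AEs.** Section 12.1.1 states that "all AEs, including pre-treatment events, are collected via the same form by investigator site staff", and section 7.1 says the same of all AE data. Under 12.2 each event is evaluated for, among other things, "action taken with the investigational intervention, outcome, and causal relationship to the investigational intervention". For possible unanticipated adverse device effects (UADEs), section 12.3.2 says that "the investigator should consider the intervention being administered, and the underlying disorder or condition of the subject".

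**What the support team does.** Sections 11.5.4 and 11.5.5 describe its members as "personnel external to the site and not involved in data collection". They also monitor use of the device (10.2) and hold the qualitative interview (11.3.7).

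**The concern.** The harms the protocol expects (4.4) are motion sickness, eye strain, headache, dizziness, nausea, and anxiety or panic set off by the stimuli. A subject can hardly report one of these usefully without saying that it arose in or after a session, and the scripted reminder, taken at its word, discourages exactly that. The person who needs the information is the one the subject has been told not to give it to. The person the subject may talk to has no written duty to pass it on.

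At stake are the count of non-serious AEs and the related/not-related summaries (Protocol 15.4.3.1; SAP 12.10.4). Protocol 4.3 says that subject monitoring in this pilot will be broadly aligned with the later registration trial, so the wording may be carried forward.

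**Working it through.** The plan gives no figure for this point, so the check is mainly a comparison of sections.

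**1. Width of the ban.** Sections 7.1 and 7.2.2 cover descriptions of the intervention. Sections 11.5.2 and 11.5.3 cover anything about it. The broader form is the one scripted for the visits. None of the four sections exempts symptoms or their timing.

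**2. What the AE form needs.** The possible, probable and definite grades in 12.2 each depend on the event following use within a reasonable time, and the not-related grade on an improbable time relation. The action-taken field includes temporary removal, which is what 4.4 expects of a subject who panics. Both fields need facts about use of the device. Session use is monitored by the support team (10.2), and no section says the site receives session times.

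**3. The other channel.** No section requires the support team to send the site a symptom heard in a support call or in the qualitative interview. The interview follows the site's Week 8 assessments by up to 48 hours (11.3.7, 11.5.4).

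**4. Timing.** AE collection at Baseline (Part 1) precedes the first session on Day 1. The next scheduled site contact is in the last three days of Week 2, Days 12 to 14, so 11 to 13 days later. Week 4 contacts fall on Days 26 to 28, so later gaps run from 26 − 14 = 12 to 28 − 12 = 16 days. The expected effects are described as transitory (4.4), and the AE question is asked without prompting (11.4.1).

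**5. Illustration only.** The documents give neither an AE rate nor a reporting fraction. Let p be an assumed true incidence of a VR-related event in an arm, r an assumed fraction reported, and n the arm size. The chance of recording at least one case is 1 − (1 − p·r)^n. The plan has n = 20 (15 / (1 − 0.25) = 20, which reproduces Protocol 15.1). SAP section 13 reports 52 subjects in the Safety Population, so an assumed equal split gives n = 26.

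| n | p | r = 1 | r = 0.8 | r = 0.5 |
|---|---|---|---|---|
| 20 | 5% | 0.64 | 0.56 | 0.40 |
| 20 | 10% | 0.88 | 0.81 | 0.64 |
| 20 | 20% | 0.99 | 0.97 | 0.88 |
| 26 | 5% | 0.74 | 0.65 | 0.48 |
| 26 | 10% | 0.94 | 0.89 | 0.74 |
| 26 | 20% | 1.00 | 0.99 | 0.94 |

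For example, 1 − 0.90^20 = 0.88 and 1 − 0.95^20 = 0.64.

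**6. Comparison between arms.** Assume true rates of 30% and 15%, with 40% withheld in both arms. The recorded rates are 0.30 × 0.6 = 18% and 0.15 × 0.6 = 9%. The difference falls from 15 to 9 percentage points, but the ratio stays at 2. Equal withholding does not make the arms look alike; that would take unequal withholding, for which the documents give no evidence.

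**The case against.** The protocol sends these harms to the site. Section 4.4 puts VR effects and elicited anxiety under normal AE reporting. Section 11.4 gives subjects the site's telephone number for safety concerns, and 7.1 adds contact details in the consent form for the same purpose. Section 11.4.1 has site staff ask about AEs at every scheduled contact and take spontaneous reports. Completed scales are also reviewed for possible AEs (11.5.4). The reminder is evidently about blinding, and device issues most naturally means technical ones, which is how 7.2.2 describes the support team's role. The reminder script, the consent text and the support-team instructions are not among the documents, so an exception may exist there.

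Most of this stands, and it rules out three stronger readings that a reader might infer:

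- **That VR harms will be missed.** The routes above are open, so loss is a risk and not a certainty.
- **That site staff may not learn when a symptom began.** No section stops them asking. Start times are used where available (15.4.3), and relation to VR use can be judged without knowing the arm.
- **That SAEs and UADEs are equally exposed.** SAEs are mostly defined by outcomes such as death or hospitalization (12.1.2), and both types are open to unblinded pharmacovigilance review (7.2.2).

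What the objection does not remove is the conflict in wording. A telephone number and an open question give access, but neither tells the subject that the ban leaves out a symptom felt in the headset. The reviewed scales (PHQ-9, PGI-I and CEQ), as described in 11.3, do not ask about VR effects. Pharmacovigilance can assess only what reaches it.

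**Conclusion.** The point holds as an internal conflict in the protocol. The scripted reminder is wider than the blinding section requires and has no exception for symptoms. It works against the staff who alone collect AEs and must grade them by timing of use. The consequence is a risk of under-reporting or weak attribution, mainly of non-serious VR-related AEs. Its size cannot be derived from the documents, and the figures above rest on assumed rates and fractions.

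A reader might also infer a bias towards finding no harm from BVR-100. That is possible but not shown: headset effects apply to both arms, and the documents do not say how far content that provokes discomfort differs between them. The primary CEQ endpoint is not touched, and safety is summarized descriptively (SAP 8.1). This should be fixed; confidence is moderate.

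**What to change.** - **Protocol 11.5.2 and 11.5.3:** replace the broad reminder with the narrower ban of 7.2.2. State in the same reminder that any symptom or distress during or after a VR session, and when it started, is exempt and should be reported to site staff.
- **Protocol 7.2.2 and 11.3.7:** require the unblinded support team to forward to the site, without content or allocation, any symptom heard in a support contact or the qualitative interview, for entry as an AE.

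The cost is a change to the reminder and to the support team's instructions, with no new visit or staff. The downside is a small chance that a symptom report hints at allocation, limited because both arms use the same headset. The change acts only on contacts still to come. With 52 subjects already in the Safety Population at the January 2024 data cutoff (SAP section 13), much of its value may lie in the later trial.
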